|-----------------|------------------|------------------|
| -1 ^a | 400 mg × 14 days | 200 mg × 14 days |
| 1 ^b | 400 mg × 21 days | 200 mg × 14 days |
| 2 | 400 mg × 21 days | 300 mg × 14 days |
| 3 | 400 mg × 28 days | 300 mg × 14 days |

a. Dose level -1 may be explored if the starting dose is not tolerated.

b. Starting dose level.

Table 3. Dose-Escalation Decision Rule

| | Number of DLT-Evaluable Subjects at Current Dose Level | | | | | | | | |
|---|--|---|---|---|----|----|----|----|----|
| Action | 6 | 7 | 8 | 9 | 10 | 11 | 12 | 13 | 14 |
| Escalate if # subjects with DLT ≤ | 1 | 1 | 1 | 1 | 1 | 1 | 2 | 2 | 2 |
| Stay at current dose if # subjects with DLT = | - | - | 2 | 2 | 2 | 2 | 3 | 3 | 3 |
| De-escalate if # subjects with DLT ≥ | 2 | 2 | 3 | 3 | 3 | 3 | 4 | 4 | 4 |
| Eliminate ^a if # subjects with DLT ≥ | 3 | 4 | 4 | 4 | 5 | 5 | 5 | 5 | 6 |

DLT = dose-limiting toxicity

As of 08 September 2022, 46 subjects were enrolled in Part 3 (Dose Finding).

Part 3: Randomization

Part 3 (Randomization) was removed from Version 6.0 of this protocol.

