The use of venetoclax + oral AZA may exacerbate complications of myelosuppression which include infections and bleeding. Venetoclax + oral AZA treatment may be interrupted, delayed, or reduced (refer to Table 8 and Appendix D) at the discretion of the investigator if the subject experiences myelosuppression-associated complications such as those described below:

- febrile neutropenia (temperature ≥ 38.5°C and ANC < 1,000/μL)
- active viral, bacterial, or fungal infection (i.e., requiring IV antiinfectives or extensive supportive care)
- hemorrhage (GI, genito-urinary, pulmonary with platelets < 25,000/ μ L, or any central nervous system hemorrhage)

Dose interruptions greater than 21 days in duration must be discussed with the AbbVie TA MD to determine if the subject may continue on study treatment.

Treatment with venetoclax + oral AZA may be resumed once the above conditions have improved or have been stabilized with adequate treatment (i.e., anti-infective therapy, transfusions, or growth factors) and toxicity has resolved to ≤ Grade 1 or has returned to baseline level. Study treatment should not be resumed for at least 3 days following resolution of fever. Complete blood and platelet counts should be performed regularly, as clinically indicated, and prior to each treatment cycle.

In the event of toxicity, a maximum of 1 dose reduction to a daily dose of 400 mg for 14 days is permitted for venetoclax. If toxicity persists in the subsequent cycle, a maximum of 1 dose reduction to a daily dose of 200 mg for 7 days is permitted for oral AZA. The decision to modify a subject's treatment schedule of venetoclax from 21 to 14 days and oral AZA from 14 to 7 days should first be discussed with the TA MD. Subjects should not receive less than 400 mg for 14 days and 200 mg for 7 days of venetoclax and oral AZA, respectively (Table 8).

Table 8. Dose Reduction for Venetoclax + Oral AZA for Subjects – Part 3: Dose Finding

| If Current Dose Level | | Then Dose Reduction Level | |
|-----------------------|------------------|---------------------------|------------------|
| Venetoclax Dose | Oral AZA Dose | Venetoclax Dose | Oral AZA Dose |
| 400 mg × 21 days | 300 mg × 14 days | 400 mg × 21 days | 200 mg × 14 days |
| 400 mg × 21 days | 200 mg × 14 days | 400 mg × 14 days | 200 mg × 14 days |
| 400 mg × 14 days | 200 mg × 14 days | 400 mg × 14 days | 200 mg × 7 days |

No further dose reductions

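### For a Part 3 subject on Dose Level 2, the dose-reduction paragraph and Table 8 reduce different drugs first and allow different numbers of reductions; Table 8 also has no row for Dose Level 3.

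*Protocol*

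**What the plan says.** The Part 3 paragraph of Protocol Section 6.2 (Dose Modifications for Venetoclax + Oral AZA) sets a two-stage rule. On toxicity, "a maximum of 1 dose reduction to a daily dose of 400 mg for 14 days is permitted for venetoclax". If toxicity persists into the next cycle, "a maximum of 1 dose reduction to a daily dose of 200 mg for 7 days is permitted for oral AZA". It then asks that the shortening of the "schedule of venetoclax from 21 to 14 days and oral AZA from 14 to 7 days should first be discussed with the TA MD", and sets the floor with a reference to Table 8: "Subjects should not receive less than 400 mg for 14 days and 200 mg for 7 days of venetoclax and oral AZA, respectively".

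Table 8 follows directly. Each row gives the current venetoclax and oral AZA regimen, then the reduced one:

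- Row 1: "400 mg × 21 days | 300 mg × 14 days | 400 mg × 21 days | 200 mg × 14 days"
- Row 2: "400 mg × 21 days | 200 mg × 14 days | 400 mg × 14 days | 200 mg × 14 days"
- Row 3: "400 mg × 14 days | 200 mg × 14 days | 400 mg × 14 days | 200 mg × 7 days"

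The table then states that no further reduction is available.

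Table 2 in Section 4.1 lists four Part 3 levels: -1, 1, 2 and 3. The highest is "3 | 400 mg × 28 days | 300 mg × 14 days". The Part 3 activity schedule in Appendix H still provides for 28-day venetoclax dosing.

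The tables are operative. The hematologic and nonhematologic paragraphs of Section 6.2 direct investigators to Tables 6, 7 and 8 when a toxicity recurs, and Appendix D refers recurrent events back to Section 6.2. A footnote to Appendix D says that a reduced dose is not raised again.

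**The concern.** The paragraph and the table sit side by side, the first cites the second, and neither is said to take precedence. For a subject on Dose Level 2 they disagree on three things: which drug is reduced first, how many oral AZA reductions are allowed, and how many steps lead to the floor. A site that follows the paragraph also reaches a regimen that Table 8 does not list. For Dose Level 3 the table offers nothing.

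This is first a safety matter. Two investigators facing the same recurrent toxicity can take different actions and both be compliant, and because reductions are not reversed, the choice fixes the subject's later exposure.

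It also affects interpretation. The Part 3 secondary objective is to characterise safety and toxicity. Exposure after Cycle 1, and adverse events leading to reduction of each drug, would mix two algorithms. The SAP supplied is written for protocol version 2.0 and does not cover Part 3. Its Section 9.2.1, however, tabulates reductions separately for venetoclax and azacitidine. If that layout is carried over, the split between the two drugs would partly reflect which rule the site read.

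**Working it through.** No sample-size or error-rate figure is involved, so there is no planned figure to reproduce. The check starts from each Table 2 level, follows each rule to its end, and compares the two paths.

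**Inputs.** Starting regimens come from Table 2 (Section 4.1). The paragraph rule and Table 8 come from Section 6.2.

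**Formula.** Per-cycle total = mg per day × dosing days per cycle.

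- Venetoclax: 400 × 28 = 11200; 400 × 21 = 8400; 400 × 14 = 5600 mg.
- Oral AZA: 300 × 14 = 4200; 200 × 14 = 2800; 200 × 7 = 1400 mg.

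**Paths** (venetoclax / oral AZA, mg per cycle):

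| Starting level | By the paragraph | By Table 8 | Agreement |
|---|---|---|---|
| -1 | 5600/2800 → 5600/1400 (1 step) | 5600/2800 → 5600/1400 (1 step) | Same |
| 1 | 8400/2800 → 5600/2800 → 5600/1400 (2 steps) | 8400/2800 → 5600/2800 → 5600/1400 (2 steps) | Same |
| 2 | 8400/4200 → 5600/4200 → 5600/1400 (2 steps) | 8400/4200 → 8400/2800 → 5600/2800 → 5600/1400 (3 steps) | Different |
| 3 | 11200/4200 → 5600/4200 → 5600/1400 (2 steps, read literally) | No row | Gap |

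**Dose Level 2 in detail.**

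- First step by the paragraph: venetoclax falls by (8400 − 5600)/8400 = 33% and oral AZA is unchanged.
- First step by the table: oral AZA falls by (4200 − 2800)/4200 = 33% and venetoclax is unchanged.
- Number of oral AZA reductions: at most one by the paragraph, two by the table (rows 1 and 3).
- Size of the oral AZA reductions: the paragraph's single step is (4200 − 1400)/4200 = 67%. The table's two steps are 33% and then (2800 − 1400)/2800 = 50%.
- The paragraph's intermediate regimen, 400 mg × 14 days plus 300 mg × 14 days, is in no row of Table 8.

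**Dose Level 3 in detail.** Table 8 has three rows and none starts from 28 days of venetoclax. Tables 6 and 7 do contain steps from 28 days to 21, but both are labelled Part 1 only. The paragraph could be applied literally, but the only venetoclax schedule change it names is from 21 days to 14.

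Wherever Table 8 has a row, both rules end at the same floor, 5600/1400 mg.

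**The case against.** The strongest reply is that the two limits of one reduction may concern only the shortening of schedules. The next sentence of the paragraph speaks of venetoclax going from 21 to 14 days and oral AZA from 14 to 7, which are exactly rows 2 and 3 of Table 8, in that order. Row 1 (oral AZA 300 to 200 mg, days unchanged) would then be a separate, earlier step. That may be the intent, but the text does not say it. The paragraph nowhere mentions a step from 300 to 200 mg at 14 days, and read as written it still starts with venetoclax.

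A second reply is that safeguards limit divergence. Reductions are at the investigator's discretion, the schedule changes are to be discussed first with the sponsor's medical director, and further reductions are possible. Such contact makes unnoticed divergence less likely, but it does not settle the order or the maximum.

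Three points on scope and reach stand:

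- The conflict between paragraph and table is confined to Dose Level 2.
- The Dose Level 3 problem is a gap, and the documents do not say that anyone was treated at that level.
- The effect on tolerability at the recommended dose arises only if that dose is Level 2 or 3, which the documents do not state. The Cycle 1 DLT endpoint is not claimed to be affected.

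Timing also matters. Part 3 had 46 subjects by 08 September 2022, and treatment is capped at 24 × 28 = 672 days. If enrolment ended then and cycles ran on time (both assumptions), the last dosing would fall in about July 2024, shortly after the protocol date of 26 April 2024. Few subjects might still face a first reduction under corrected wording, although those already reduced still have to be summarised.

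**Conclusion.** The concern holds. For a Dose Level 2 subject, Section 6.2 contains two stated rules that cannot both be followed. They differ in the drug reduced first, in the number of oral AZA reductions (one against two) and in the steps to the floor (two against three). After the first reduction the regimens differ by 2800 mg of venetoclax and 1400 mg of oral AZA per cycle, in opposite directions. Separately, Table 8 omits Dose Level 3, and no other reduction table applies to Part 3.

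This rests on a literal reading of the paragraph and on Table 8 being complete as printed: it shows three rows and a closing line, with no sign of damage. The number of subjects affected is unknown, because the documents give no count per dose level. The totals show that the two paths differ; they do not show that harm or bias occurred. Since this is a contradictory instruction for handling toxicity, it should be corrected and not left to case-by-case discussion.

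**What to change.** Reconcile the Part 3 paragraph of Section 6.2 with Table 8 so that together they give one sequence and one maximum number of reductions per drug. Extend the result to every regimen in Table 2, including Dose Level 3, or state explicitly that Dose Level 3 will not be used. If the limits in the paragraph were meant to apply only to schedule shortening, say so and name the oral AZA strength reduction separately. Which order or dose is right is for the sponsor's clinical team; none is proposed here.

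In the analysis it would help to record which sequence each reduced Part 3 subject received, and to show it alongside the summaries of dose reduction and exposure. This flag is optional and is not needed to correct the protocol.

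The cost is a clarification letter or amendment wording and, if adopted, one derived variable. No additional subjects or data collection are required.

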6.3 Dose-Limiting Toxicity Criteria

Part 1 (Dose Confirmation) and Part 3 (Dose Finding)

Any of the following events during Cycle 1, which are considered possibly or probably related to the administration of venetoclax, will be considered a DLT:

- Hematologic toxicities
 - any Grade ≥ 3 neutropenia lasting more than 7 days
 - any Grade ≥ 3 thrombocytopenia lasting more than 7 days
- Nonhematologic toxicities
 - any Grade 3 AE lasting ≥ 72 hours except for Grade 3 hypersensitivity reactions or Grade 3 localized injection-site toxicities
 - Grade ≥ 3 nausea, diarrhea, or vomiting despite adequate/maximal medical intervention lasting more than 7 days (Part 3 only)
 - any Grade ≥ 4 AE
 - any Hy's law cases defined as elevated aspartate aminotransferase (AST) or alanine aminotransferase (ALT) ≥ 3 × ULN with concurrent elevated total bilirubin ≥ 2 × ULN in the absence of elevated alkaline phosphatase or other conditions that could cause these laboratory abnormalities

In addition, AEs not meeting above criteria but lead to omitting > 20% of the scheduled dose within the cycle should be considered as a DLT unless clearly related to underlying disease.

Treatment delay due to toxicity lasting greater than 14 days since the last dose of venetoclax will also be considered DLT.

Any DLT will require an interruption and possible discontinuation of venetoclax or AZA. Venetoclax may be reintroduced at a reduced dose if the toxicity grade returns to ≤ Grade 1 or to baseline if Grade 2 at study entry. If the subject is considered to be acceptable for resumption of venetoclax dosing at the same dose or reduced dose on Day 7 of the dose interruption, the event should not be designated as a DLT.

To be considered DLT-evaluable in Part 3, subjects must complete at least 80% of assigned venetoclax dosing and oral AZA dosing in Cycle 1 or experience a DLT in Cycle 1.

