3.1 Primary Endpoint

Part 1 (Dose Confirmation)

The primary endpoint is DLTs of venetoclax in combination with AZA.

Part 3 (Dose Finding)

The primary endpoint is DLTs of venetoclax in combination with oral AZA.

Part 3 (Randomization)

Not applicable; Part 3 (Randomization) was removed from Version 6.0 of this protocol.

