5.7 Study Drug

Study drugs refer to drugs that are used (or can be used) in this study to assess the safety and the efficacy of the Investigational Product. Investigators will assess the relationship of AEs to the use of study drugs (see Table 5 for the list of study drugs).

Venetoclax manufactured by AbbVie will be administered orally, QD for each 28-day cycle beginning on Day 1 for subjects in Part 1 (Dose Confirmation) and Part 3 (Dose Finding).

If vomiting occurs after taking venetoclax, another dose should not be taken that day. In cases where a dose of venetoclax is missed or forgotten, the subject should take the forgotten dose as soon as possible, provided that the dose is taken within 8 hours of the missed dose and is taken with food and water. Otherwise, the missed dose should not be taken and the subject should take the next dose at the next scheduled dosing time.

AZA will be administered SC or IV, QD on Days 1 to 5 of each 28-day cycle, for up to 6 cycles (refer to Operations Manual Section 6.1) for subjects in Part 1. AZA must be prepared and administered by the route indicated in the package insert, prescribing information, local SmPC, or equivalent.

Oral AZA will be administered QD on Days 1 to 14 of each 28-day cycle for up to 24 cycles for subjects in Part 3. Subjects will be trained to self-administer oral AZA (refer to Operations Manual Section 6.1).

If vomiting occurs after taking oral AZA, a second dose should not be taken that day as subjects must not take 2 doses on the same day.

In cases where a dose of oral AZA is missed or forgotten, the subject should take the forgotten dose as soon as possible and resume the normal schedule in the following day.

The investigational medicinal products for this study are venetoclax, AZA, and oral AZA. AbbVie will supply venetoclax, AZA, and oral AZA. AbbVie-provided study drug should not be substituted or alternately sourced unless otherwise directed by AbbVie. AbbVie will not supply drugs other than venetoclax, AZA, and CC486. Non-investigational medicinal product (i.e., BSC) must be obtained commercially. AbbVie will not provide or reimburse for treatments administered for BSC.

If a subject is unable to come to the study site to pick up their study drug due to COVID-19, a direct-to-patient (DTP) study drug shipment can be made from the study site to the subject if allowed by local

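### The DLT list in Section 6.3 requires relatedness to venetoclax, while the primary endpoint is DLTs of the combination, so some Cycle 1 events attributed to azacitidine alone can go uncounted

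*Protocol*

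**What the plan says.** Section 3.1 of the protocol states for Part 3: "The primary endpoint is DLTs of venetoclax in combination with oral AZA". The Part 1 endpoint is worded the same way with AZA.

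Section 6.3 applies to both parts. It lists hematologic and nonhematologic criteria for Cycle 1 events "which are considered possibly or probably related to the administration of venetoclax, will be considered a DLT". AZA and oral AZA are not named in that condition. Elsewhere the section treats both drugs as relevant:

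- Grade 3 nonhematologic events lasting 72 hours or more count "except for Grade 3 hypersensitivity reactions or Grade 3 localized injection-site toxicities", yet Section 5.7 says venetoclax "will be administered orally, QD for each 28-day cycle beginning on Day 1".
- "Any DLT will require an interruption and possible discontinuation of venetoclax or AZA".

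Two further clauses need no attribution to venetoclax. The omission clause covers "AEs not meeting above criteria but lead to omitting > 20% of the scheduled dose within the cycle", with an exception for events plainly due to the leukemia. The delay clause reads: "Treatment delay due to toxicity lasting greater than 14 days since the last dose of venetoclax will also be considered DLT".

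One clause removes events whatever their attribution: if the subject is judged "acceptable for resumption of venetoclax dosing at the same dose or reduced dose on Day 7 of the dose interruption", the event is not a DLT.

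Section 6.1 gives a two-category causality scale (reasonable possibility, or none). It has no separate grades for possible and probable.

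**The concern.** The DLT count decides the recommended dose of a combination. In Part 3 it is compared with a 20% target through Table 3; in Part 1 it must fall below 20%. Some of these decisions concern azacitidine alone. Part 3 Level 1 to Level 2 raises oral AZA from 200 mg to 300 mg with venetoclax unchanged (Table 2), and the first Part 1 step down lowers AZA from 50 to 36 mg/m² with venetoclax unchanged (Table 1). A count that can leave out toxicity attributed to azacitidine alone is a weak basis for those steps.

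The error runs one way. An uncounted subject stays in the denominator as a non-DLT, so the observed rate can be too low but not too high.

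**Working it through.** **1. The decision rules (Section 4.1).** Table 3 reproduces from the stated interval (16.9%, 25.1%). At n=6, 1/6 = 16.7% is at or below 16.9%, so escalate; 2/6 = 33.3% is at or above 25.1%, so de-escalate. At n=7, 1/7 = 14.3% and 2/7 = 28.6% give the same actions. All 18 escalate and de-escalate counts match. The nine elimination counts also match if a uniform prior and a 95% cutoff are assumed. In Part 1, 3/20 = 15% meets the rule and 4/20 = 20% does not. One subject can therefore decide at these sizes.

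**2. What the omission clause catches.** Assume that omission is judged per drug (the protocol does not say which drug's schedule applies), that dosing is full until the stop, and that both drugs are interrupted as in Appendix D.

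An event not released by the Day 7 clause keeps the subject off drug for at least seven days. If seven venetoclax doses fall within the schedule, the omission is 7/28 = 25.0%, 7/21 = 33.3% or 7/14 = 50.0%, all above 20%, so the event counts. Only stops near the end of scheduled dosing escape. With a stop from Day d to the end of an L-day schedule, L − d + 1 doses are lost:

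| Venetoclax schedule | Levels | Last stop caught | First stop missed |
|---|---|---|---|
| 28 days | Part 1 Levels 1, −1; Part 3 Level 3 | Day 23: 6/28 = 21.4% | Day 24: 5/28 = 17.9% |
| 21 days | Part 1 Levels −2, −3; Part 3 Levels 1, 2 | Day 17: 5/21 = 23.8% | Day 18: 4/21 = 19.0% |
| 14 days | Part 3 Level −1 | Day 12: 3/14 = 21.4% | Day 13: 2/14 = 14.3% |

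From the day in the last column, an azacitidine-only event counts only through the delay clause. Section 6.3 does not say whether a subject who never restarts falls under that clause.

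**3. The denominator.** At Part 3 Levels 1 and 2, a subject stopped on Day 18 has taken 17/21 = 81.0% of venetoclax and 14/14 of oral AZA. That meets the 80% requirement, so the subject is DLT-evaluable and enters Table 3 as a non-DLT.

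**4. If treatment is not interrupted.** Section 6.2 makes withholding discretionary, whereas Appendix D directs interruption. If doses are not withheld, neither clause is triggered and an azacitidine-only event can go uncounted at any time in Cycle 1.

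**5. Illustration. Every rate is assumed; the documents give none.** Take 10% of subjects with a venetoclax-attributed event, an independent a = 5% with an azacitidine-only listed event, and onset uniform over 28 days. Treat every azacitidine-only event in a fraction f of the cycle as uncounted.

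- Either drug: 1 − 0.9(1 − a) = 1 − 0.9 × 0.95 = 0.145.
- As counted: 1 − 0.9(1 − a(1 − f)).
- Part 3 Levels 1–2, Days 18–21, f = 4/28: counted rate 0.1386. P(at most 1 of 6) = (1 − p)^6 + 6p(1 − p)^5 = 0.803 as counted, against 0.788 for either drug.
- Part 1, 28-day venetoclax, Days 24–28, f = 5/28: counted rate 0.1370. P(at most 3 of 20) = 0.710 as counted, against 0.672 for either drug.
- Expected uncounted subjects: 6 × 0.9 × 0.05 × 4/28 = 0.04, and 20 × 0.9 × 0.05 × 5/28 = 0.16.

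**The case against.** **The endpoint may mean DLTs of venetoclax when given with azacitidine, with Section 6.3 as its operational form.** The wording allows this. It fits poorly with dose steps that change only azacitidine, with an injection-site exemption for an oral drug, and with a DLT that may interrupt either drug. It does not remove the need to reconcile the sections.

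**The required attribution is unlikely.** The investigator must judge venetoclax not even possibly related while blaming azacitidine. Section 6.2 ascribes neutropenia to all three drugs. In the windows above, oral AZA ended at least 18 − 14 = 4 days earlier at Part 3 Levels 1–2, and AZA 24 − 5 = 19 days earlier on the 28-day schedule in Part 1. This stands and is the main reason to expect a small effect. The timing argument does not help at Part 3 Level −1, where both drugs are scheduled for 14 days.

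**The one-subject argument is selective.** Table 3 has a stay value from n=8. About 12 subjects are planned at the preliminary RPTD and at least 12 more in expansion, and Part 1 enrolled 66. This also stands: a single decision at n=6 is not the whole safety basis.

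**Stronger readings that the documents do not support.** A reader might infer that azacitidine toxicity is not counted at all. Under the same assumed rates the counted rate would then be 10%, giving 0.886 against 0.788 at n=6 and 0.867 against 0.672 at n=20. That ignores the two attribution-free clauses and the joint interruption in Appendix D. A reader might also count events starting on the planned off-drug Days 22–28 at Part 3 Levels 1–2, with Cycle 2 begun on time, as missed DLTs. Such a subject had no interruption, although Section 6.3 says a DLT requires one, and was fit to dose sooner than someone released by the Day 7 clause. How that clause applies on off-drug days is unclear, so these days are left out of the illustration.

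**Conclusion.** The concern holds in a limited form. The attribution condition in Section 6.3 is narrower than the endpoint in Section 3.1, and its relatedness terms do not match the causality scale in Section 6.1. The result can only understate the DLT rate held against 20%.

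The gap is confined to late stops only if both drugs are interrupted as in Appendix D; under the discretion in Section 6.2 it can arise earlier. The illustration is therefore neither an estimate nor an upper limit. It shows shifts of about 1 to 4 percentage points in the decision probabilities at an assumed 5% azacitidine-only rate. The true size cannot be computed from the documents and is probably small.

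A reader might infer that the RPTD was chosen wrongly. Nothing in the documents shows that, since they report no DLT counts and no attribution data. The point should be fixed because the count feeds the primary endpoint and the remedy is cheap.

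**What to change.** 1. Reconcile Sections 3.1, 6.1 and 6.3: state which drug or drugs the attribution covers, on the two-category scale of Section 6.1. State also how the Day 7 clause applies on planned off-drug days, and reconcile Section 6.2 with Appendix D on interruption. Which clinical rule applies is for the sponsor to decide.
2. Add one supplementary table by dose level of subjects with Cycle 1 events meeting the listed criteria, with the Day 7 clause applied equally, counted (a) as related to venetoclax and (b) as related to either study drug. Report the RPTD conclusion against both counts.

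The data should exist. Section 5.7 calls for relationship assessment to the study drugs, and its Table 5 includes oral azacitidine. Confirm that this was recorded per drug in Part 3; SAP Section 9.2.1 shows it only for Part 1 and Arm A. No planned output supplies the table: the summaries in protocol Section 7.4 and SAP Section 9.2.1 apply no Cycle 1 or duration condition, and the SAP is written for protocol version 2.0, without the oral AZA part.

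The cost is a wording clarification and one small table. The downside is that count (b) is post hoc, since the enrolment figures date from 2021 and 2022, and it can only equal or exceed count (a). No dose decision is reopened and no clinical rule is proposed.

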The investigator should contact the TA MD before discontinuing a subject from the study for a reason other than "planned per protocol," to ensure all acceptable mitigation steps have been explored.

Refer to the Operations Manual in Appendix J for details on how to handle study activities/procedures.

Interruption/Discontinuation of Study Drug Due to COVID 19 Infection

During the study drug dosing period, a subject with confirmed (viral test positive) or suspected COVID-19 infection can only be dosed with study drug if the following COVID-19 viral clearance criteria are met:

 At least 10 days since first positive test result have passed in asymptomatic subjects or at least 10 days since recovery, defined as resolution of fever without use of antipyretics and improvement in symptoms.

Delays in study drug dosing due to the above COVID-19 testing guidance for subjects must be discussed with the AbbVie TA MD, along with the possibility of premature discontinuation from the study drug dosing period. Follow guidelines in Section 5.6 for subjects who discontinue study drug.

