Any time during the study, if the subject must undergo emergency surgery, the study drug(s) should be interrupted at the time of the surgery. After emergency surgery, allow reintroduction of study drug(s) once the physician has examined the surgical site and determined that it has healed and there is no sign of infection.

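### The >20% dose-omission DLT rule has no drug-relatedness test, so a COVID-19 AE judged unrelated to study drug counts as a DLT when the Section 5.5 hold starts early enough in Cycle 1

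*Protocol*

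**What the plan says.** Protocol Section 6.3 defines DLTs for Part 1 and Part 3 (Dose Finding) together. The bulleted list opens with a causality condition: "Any of the following events during Cycle 1, which are considered possibly or probably related to the administration of venetoclax, will be considered a DLT". A separate paragraph after the list adds that "AEs not meeting above criteria but lead to omitting > 20% of the scheduled dose within the cycle should be considered as a DLT". Its one exception is in its closing words: "should be considered as a DLT unless clearly related to underlying disease".

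The same section removes the DLT label when the subject is fit to resume venetoclax "on Day 7 of the dose interruption, the event should not be designated as a DLT". For Part 3 only, it sets an evaluability rule: "subjects must complete at least 80% of assigned venetoclax dosing and oral AZA dosing in Cycle 1 or experience a DLT in Cycle 1".

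Protocol Section 5.5 says that a subject with confirmed or suspected COVID-19 "can only be dosed with study drug if the following COVID-19 viral clearance criteria are met". The criteria are "At least 10 days since first positive test result have passed in asymptomatic subjects or at least 10 days since recovery". Section 5.5 does not say how such a hold bears on DLT status.

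DLTs are the primary endpoint of both parts (Section 3.1). They drive Table 3 in Part 3 and the 20% rule in Part 1 (Section 4.1). The SAP supplied is version 1.0, written for protocol version 2.0. It has no DLT analysis and no Part 3, so it does not settle the point.

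**The concern.** The omission rule applies to AEs that fail the listed criteria, and an event can fail them by being unrelated to venetoclax. Section 6.1 defines an AE without requiring a causal link, and Section 2.2 refers to COVID-19 in terms of AEs. Read together, Sections 5.5 and 6.3 turn a protocol-required hold for an unrelated infection into a primary-endpoint event.

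In Part 3 the alternative classification is a non-evaluable subject. The DLT label thus turns a subject who carries no information about the dose into evidence against it. In cohorts of 6 or 7 a single count separates escalation from de-escalation. In Part 1 a single count can decide whether a further reduced-dose cohort is opened. For events with no drug contribution, the result is an inflated DLT rate and a recommended dose that may be set too low.

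**Working it through.** **1. The plan's decision table.** With the interval (16.9%, 25.1%) from Section 4.1, escalate at or below floor(0.169n) and de-escalate at or above ceil(0.251n).
- n=6: 1.014 gives 1, and 1.506 gives 2.
- n=7: 1.183 gives 1, and 1.757 gives 2.
- n=8: 1.352 gives 1, and 2.008 gives 3.
- n=12: 2.028 gives 2, and 3.012 gives 4.

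These two rows of Table 3 reproduce for every n from 6 to 14. There is no stay outcome at n=6 or 7. At n=8 to 14 there is one stay value, so one extra DLT moves the decision by one step at most.

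**2. Does the hold cross 20%?** For d scheduled days, the rule needs floor(0.2d)+1 missed days. The latest qualifying first missed day is d minus that number, plus 1.

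| Scheduled days | Missed days needed | Latest first missed day | A full 10-day hold omits |
|---|---|---|---|
| 28 | 6 | Day 23 | 10/28 = 36% |
| 21 | 5 | Day 17 | 10/21 = 48% |
| 14 | 3 | Day 12 | 10/14 = 71% |

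A later start does not trigger the rule. Section 6.3 does not say which drug's scheduled dose is meant; the 14-day row applies to oral AZA, or to venetoclax at dose level -1.

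**3. Does the Day 7 sentence remove the label?** If the infection is symptomatic, the 10 days run from recovery, so dosing is still barred on Day 7. If it is asymptomatic and the hold starts at the positive test, Day 7 again falls short of 10 days. If dosing stops about 10 - 7 = 3 or more days after the test, Day 7 can satisfy both rules.

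**4. Effect of one case.**
- Part 3, n=6: 2/6 as written is de-escalate. With the subject excluded it is 1/5, and after a DLT-free replacement 1/6, which is escalate.
- Part 1: 3/20 = 15% establishes the dose; 4/20 = 20% calls for another cohort.

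**5. Illustration.** The documents give neither input, so both are assumed: a true DLT rate p = 0.15, and a per-subject chance q of a qualifying unrelated hold in Cycle 1 of 5% (range 1% to 10%).
- As written, the DLT rate is 1 - (1-p)(1-q). At q = 0.05 this is 1 - 0.85 × 0.95 = 0.1925.
- With exclusion and replacement (drug-caused DLTs still counted), the rate among evaluable subjects is p/(1-(1-p)q). At q = 0.05 this is 0.15/(1 - 0.85 × 0.05) = 0.157.

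Exact binomial results:

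| q | P(2 or more of 6), as written | P(2 or more of 6), excluded and replaced | P(3 or fewer of 20), as written | P(3 or fewer of 20), excluded and replaced |
|---|---|---|---|---|
| 1% | 24.4% | 22.7% | 61% | 64% |
| 5% | 33% | 24% | 44% | 62% |
| 10% | 43% | 26% | 27% | 58% |

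Part 1 has no evaluability rule. If the held subject is kept there as a non-DLT, the pass probability is 65% at every q.

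**The case against.** **The rule may be deliberate caution.** Section 2.2 says that subjects on the combination may be at increased risk of COVID-19 or of serious illness if infected. Section 6.2 lists active viral infection among complications of myelosuppression. Counting dose-limiting AEs unless the underlying disease clearly explains them is a defensible stance. This stands for infections with a possible drug contribution, and they should go on counting. It does not justify counting an event that the investigator has judged unrelated.

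**The causality condition may be meant to cover the whole section.** That reading is possible. The separate paragraph, its application to events outside the list and its own exception all point the other way. At best the primary endpoint is ambiguous.

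**Stronger readings that the documents do not support.**
- A reader might infer that every COVID-19 hold becomes a DLT. The rule needs an AE, and under Section 6.1 an asymptomatic positive test need not be one. Late onset also escapes the rule.
- A reader might infer that the Day 7 sentence can never help. It can in some asymptomatic cases, as shown above.
- A reader might treat emergency surgery as equivalent, because "if the subject must undergo emergency surgery, the study drug(s) should be interrupted at the time of the surgery". Section 6.2 sets no minimum duration for that hold, so crossing 20% and missing Day 7 depend on the case.
- A reader might infer that the recommended dose has in fact been biased. The documents give enrolment counts at two dates, not enrolment windows or DLT causes, and do not show when the COVID-19 hold was introduced. Section 5.5 refers to the Operations Manual for COVID-19 mitigation and handling, and that manual was not available for this review.

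**The size rests on an assumed hold rate.** This is correct. Section 5.1 excludes known active infection at entry, and at a 1% rate the n=6 difference is under 2 percentage points.

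**Conclusion.** The concern holds for a defined class of event: a COVID-19 AE in Cycle 1, judged unrelated to study drug, with a hold that starts early enough to omit more than 20% of the dose and that the Day 7 sentence does not cover. For that class, Section 6.3 as written gives the wrong classification on the primary endpoint and biases DLT rates upward. It does not establish a general downward bias in the recommended dose.

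One case is enough to reverse a decision at n=6 or 7, or to tip a Part 1 cohort of 20. At the assumed 15% DLT rate and 5% hold rate, the as-written rule adds about 9 percentage points to the chance of de-escalating at n=6 (32.6% - 23.9% = 8.7). It takes about 17 points off the chance that a Part 1 cohort passes (61.5% - 44.5% = 17.0). These sizes scale with the assumed hold rate. The conflict between the two sections does not depend on it.

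**What to change.** 1. Reconcile Sections 5.5 and 6.3. Extend the omission-rule exception to AEs assessed, on the Section 6.1 causality scale, as having no reasonable possibility of relation to either study drug. Keep the individual causality assessment, so that infections judged possibly drug-related still count.
2. State how such subjects are handled. In Part 3 they are non-evaluable under the existing 80% rule and are replaced. For Part 1, say explicitly whether they are replaced or kept in the denominator as non-DLTs, since that part has no evaluability rule.
3. State which drug's scheduled dose the 20% refers to.
4. With 66 and 46 subjects already enrolled, new wording alone may change no decision. Identify every DLT that arose only through the omission rule, adjudicate its causality, and report the DLT rate per dose level with and without the unrelated ones. This shows whether either recommended dose depends on them.

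The change concerns endpoint classification only; no dose, hold or resumption rule is altered. It costs one clause, one statement per part and the adjudication of what may be only a few cases. The price is an occasional replaced subject and a slightly less conservative DLT count.
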